7.2. Participant Discontinuation/Withdrawal from the Study

A participant may withdraw from the study

- at any time at his or her own request
- at the request of his or her designee (for example, parents or legal guardian)
- at the discretion of the investigator for safety, behavioral, compliance, or administrative reasons
- if the participant becomes pregnant during the study
- if enrollment in any other clinical study involving an investigational product or enrollment in any other type of medical research judged not to be scientifically or medically compatible with this study, and
- if the participant, for any reason, requires treatment with another therapeutic agent that has been demonstrated to be effective for treatment of the study indication, discontinuation from the study occurs prior to introduction of the new agent.

At the time of discontinuing from the study, if possible, an early discontinuation visit should be conducted, as shown in the SoA. See SoA for data to be collected at the time of study discontinuation and follow-up and for any further evaluations that need to be completed. The participant will be permanently discontinued both from the study intervention and from the study at that time.

If the participant withdraws consent for disclosure of future information, the sponsor may retain and continue to use any data collected before such a withdrawal of consent. If a participant withdraws from the study, he or she may request destruction of any samples taken and not tested, and the investigator must document this in the site study records.

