6.3. Measures to Minimize Bias: Randomization and Blinding

This is a double-blind study.

Participants who meet all criteria for enrollment will be randomly assigned to 1 of the study treatment arms at Visit 4. Assignment to treatment arms will be determined by a computer-generated random sequence using an IWRS. Participants will be randomly assigned in a 2:1:1:1:1:2:2 ratio (LY3437943 1 mg QW, LY3437943 4 mg QW (a), LY3437943 4 mg QW (b), LY3437943 8 mg QW (a), LY3437943 8 mg QW (b), LY3437943 12 mg QW, placebo QW).

Although the participant and the investigator will know the injection volume of study drug, they will not know whether the participant is receiving LY3437943 or placebo. To preserve the blind, participants randomized to placebo will be randomly assigned to follow the injection dose schedule for 1 of the LY3437943 treatment arms.

To preserve the blinding of the study, a minimum number of Lilly personnel will see the randomization table and treatment assignments before the study is complete.

Emergency unblinding may be performed through the IWRS. This option may be used ONLY if the participant's well-being requires knowledge of the participant's treatment assignment. All unblinding events are recorded and reported by the IWRS.

If an investigator, site personnel performing assessments, or participant is unblinded, the participant must be discontinued from the study. In cases where there are ethical reasons to have the participant remain in the study, the investigator must obtain specific approval from a sponsor

clinical research physician (CRP) or clinical research scientist (CRS) for the participant to continue in the study.

In case of an emergency, the investigator has the sole responsibility for determining if unblinding of a participant's treatment assignment is warranted for medical management of the event. The participant's safety must always be the first consideration in making such a determination. If a participant's treatment assignment is unblinded, Lilly must be notified immediately. If the investigator decides that unblinding is warranted, it is the responsibility of the investigator to promptly document the decision and rationale and notify Lilly as soon as possible.

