7.1. Discontinuation of Study Intervention

In rare instances, it may be necessary for a participant to permanently discontinue (definitive discontinuation) study drug. If study drug is definitively discontinued, the participant will remain in the study to be evaluated for all planned efficacy and safety measures. In addition, the participant may continue to receive diet and physical activity counseling. Participants who are unwilling to attend all scheduled visits after stopping study drug will be asked to return for a final visit 48 weeks after randomization, primarily for weight measurement and assessment of AEs (Visit 99). If participants are unwilling to attend Visit 99, their refusal to attend should be documented in the participant medical record. See the SoA for data to be collected at the time of discontinuation of study drug and follow-up and for any further evaluations that need to be completed.

Possible reasons leading to permanent discontinuation of study drug:

- **participant decision**
 - the participant requests to discontinue study drug
- **clinical considerations**
 - initiation of prohibited concomitant medications (see Section 6.5) if participants will not or cannot discontinue them
 - intolerable GI symptoms despite management as described in Section 6.5.1 and Section 6.6.1

Note: The investigator should contact the Sponsor CRP/CRS to discuss whether it is medically appropriate for the participant to continue study treatment.

- if the investigator, after consultation with the sponsor-designated medical monitor, determines that a systemic hypersensitivity reaction has occurred related to study drug administration, the participant should be permanently discontinued from the investigational drug
- BMI \leq 19 kg/m² is reached at any time during the treatment period
- diagnosis of T1D
- diagnosis of MTC or MEN2 after randomization
- significant elevation of calcitonin (Section 8.3.2.3.1)
- diagnosis of acute or chronic pancreatitis
- diagnosis of an active or untreated malignancy (other than basal or squamous cell skin cancer, in situ carcinomas of the cervix, or in situ prostate cancer) after randomization
- onset of pregnancy in a female participant

- occurrence of any other treatment-emergent AE (TEAE), SAE, or clinically significant finding for which the investigator believes that permanent study drug discontinuation is the appropriate measure to be taken
- PHQ-9 score ≥ 15

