- Category 1: data collected after these ICEs are excluded. The resulting missing values can be imputed using those participants who adhere to the study medication in the same treatment group under the assumption of Missing At Random (MAR).
- Categories 2 and 4: data collected after these intercurrent events will be used. Additional missing values will be imputed by using the observations for those who discontinue study treatment due to these corresponding ICEs and who have data collected post these ICEs (retrieved dropout approach) or by jump to reference (placebo imputation) under the assumption of Missing Not At Random (MNAR).
- Category 3: data after initiation of the ICEs will be excluded. Since anti-obesity medication other than LY3437943 is prohibited until the participants discontinue the study treatment, we assume that the ICEs of such treatment discontinuation associated with the use of anti-obesity medication belong to the Categories 2 or 4, e.g., study treatment discontinuation due to lack of efficacy. The resulting missing values will be imputed using the strategies as defined in Category 2 and 4.

The alternative methods of handling ICEs and imputing missing values are summarized in [Table GZBF.4.3](#).

Table GZBF.4.3. Strategy to Handle ICE and Missingness for Hybrid Estimand

Type of ICE	Strategy to handle ICE	Potential outcome	Handling data after ICE	Missing data imputation
Category 1	Hypothetical	The outcome if participants would adhere to the study medication	To discard	Imputing using the observed data up to ICEs from the same treatment group, based on the MAR assumption
Category 2	Treatment policy	The outcome as the result of ICE	To use	Imputing using retrieved dropouts or placebo arm,
Category 3	Hypothetical	The outcome if participants would not	To discard	

Type of ICE	Strategy to handle ICE	Potential outcome	Handling data after ICE	Missing data imputation
		take anti-obesity medication		based on MNAR assumption
Category 4	Treatment policy	The outcome as the result of ICE	To use	

Abbreviations: ICE = intercurrent event; MAR = missing at random; MNAR = missing not at random.

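### Protocol 7.2 conflicts with 7.1 and SAP 4.3.3 on whether a participant who starts another weight-loss agent stays in the study; separately, 6.3 makes study exit the default after unblinding

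*Protocol*

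**What the plan says.** **Stopping study drug (Protocol 7.1).** The general rule is: "If study drug is definitively discontinued, the participant will remain in the study to be evaluated for all planned efficacy and safety measures". One listed reason for stopping drug is starting a prohibited concomitant medication that the participant will not or cannot give up. Protocol 6.5 gives other weight-management medications as its example of what is not allowed.

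**Leaving the study (Protocol 7.2).** The list opens permissively: "A participant may withdraw from the study". Its last item covers a participant who needs another agent shown to be effective for the study indication, and there "discontinuation from the study occurs prior to introduction of the new agent". The section then asks for an early discontinuation visit where possible and adds: "The participant will be permanently discontinued both from the study intervention and from the study at that time".

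**Unblinding (Protocol 6.3).** "If an investigator, site personnel performing assessments, or participant is unblinded, the participant must be discontinued from the study". An exception follows: "In cases where there are ethical reasons to have the participant remain in the study, the investigator must obtain specific approval" from a sponsor physician or scientist.

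**SAP 4.3.3.** The alternative version of the hybrid estimand has a Category 3 for use of anti-obesity medication after permanent treatment discontinuation. Its reasoning begins: "Since anti-obesity medication other than LY3437943 is prohibited until the participants discontinue the study treatment". It therefore expects some participants to be off study drug, still followed, and starting another agent.

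**The concern.** A site whose participant needs another weight-loss drug finds two instructions. Under 7.1 the participant stops study drug and keeps attending. Under 7.2 the participant leaves the study before the new drug begins. Sites could reasonably act differently, and the SAP plans for an event that one of the two instructions would prevent anyone from observing.

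The unblinding rule raises a related question. Protocol 6.3 allows emergency unblinding only when the participant's well-being requires it, so these exits are likely to follow safety events and to be informative.

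At stake is the fit between data collection and the estimands that look beyond study drug. SAP 1.1 defines the safety estimand over the treatment and follow-up periods whatever the adherence. Protocol 8.3.1 stops adverse-event collection when participation ends, and SAP 4.1 excludes from analysis any data dated after the end of participation. An exit from the study, unlike an exit from drug, removes what the safety estimand asks for.

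**Working it through.** **1. Is it the same event in 7.1 and 7.2?** A drug effective for the study indication is a weight-management drug. Protocol 6.5 names that class as not allowed, and 7.1 lists starting a prohibited medication as a reason to stop study drug. The item in 7.1 is broader, since it covers every prohibited medication, but the event in 7.2 lies inside it. For that event 7.1 keeps the participant in the study and 7.2 does not.

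**2. SAP against 7.2.** If participants always leave the study before the new agent starts, its use after treatment discontinuation is never recorded. Category 3 of the alternative hybrid would then be empty by design.

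**3. Unblinding against 7.1.** Protocol 7.1 does not mention unblinding. Protocol 6.3 is thus a specific rule that departs from a general principle, not a contradiction of a listed item.

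**4. Which analyses would use the lost data?**

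| Analysis | Treatment of later data | Effect of study exit |
|---|---|---|
| Primary efficacy estimand (SAP 4.3) | Only data before permanent discontinuation are used | None |
| Main hybrid, Category 2, lack of efficacy (SAP Table 4.2) | Set to missing | None |
| Main hybrid, Category 3 (SAP 1.1, Table 4.2) | Treatment policy: later weights are used | Weights lost |
| Alternative hybrid, anti-obesity drug (SAP 4.3.3) | Excluded once the drug starts | Weights not needed, but the event goes unrecorded |
| Safety estimand (SAP 1.1) | Used whatever the adherence | Routine adverse events lost |

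SAP Table 4.1 has no row for unblinding. It puts adverse events and other reasons in Category 3, so most unblinding exits would probably fall there. For that category the SAP already expects too few retrieved dropouts and falls back on jump-to-reference imputation.

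**5. Size.** The documents give no rate for either event. I assume 1-5% for both together.

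- Participants: 0.01 × 300 = 3; 0.05 × 300 = 15.
- Completers as planned (Protocol 9.2): 300 × 2/10 × 0.8 = 48 per dose and placebo.
- Planned power, with difference 8 and SD 10: SE = 10 × √(2/48) = 2.041; 8/2.041 = 3.92; 3.92 − 1.96 = 1.96, giving 97.5% (97.2% with the exact t distribution). The stated figure of at least 97% is reproduced.
- If the exits came on top of the 20% dropout, n = 60 × (1 − 0.20 − f). For f = 1%, 2% and 5% this is 47.4, 46.8 and 45 per group, with t-test power of 97.1%, 96.9% and 96.4%.
- Main hybrid: if a fraction f of an active arm is imputed as placebo, a difference of 8 becomes 8 × (1 − f), which is 7.92 at 1% and 7.6 at 5%. This counts as error only so far as true off-drug weights differ from placebo.

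Power is not the issue. Consistency, and data for the safety estimand, are.

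**The case against.** A reader might infer that both rules force participants out in contradiction of 7.1. The documents do not support that. The list in 7.2 opens with a permissive verb, and 6.3 has a sponsor-approved route to stay. Overlap between the lists is not in itself a conflict: pregnancy appears in both, as a reason to stop drug and as a reason a participant may leave. What stands against this defence is that the new-agent item carries its own declarative clause on timing and is followed by a sentence ending drug and study together.

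A reader might also infer that the hybrid estimands depend on all of these weights. They do not. The alternative version, which itself is only optional, discards weights once an anti-obesity drug starts, and the main version discards them after discontinuation for lack of efficacy. The need is limited to Category 3 of the main version.

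Finally, a reader might conclude that all later follow-up disappears. That is too strong. The early discontinuation visit includes weight and adverse events. Protocol 8.3 has serious and special-interest events followed to resolution or stabilization, and keeps investigators responsible for events that are related or led to stopping drug. Protocol 8.3.1 still takes reports of serious events learned of after participation ends. What goes is routine collection of new events after exit. By SAP 4.1, data dated after the end of participation also stay out of the analyses, even where they have been reported.

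**Conclusion.** The point holds in a limited form. There is one direct conflict: 7.2 against 7.1 and SAP 4.3.3 on a participant who starts another weight-loss agent. There is one departure from principle: study exit as the default after unblinding in 6.3, with an exception.

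The consequence is mainly a gap in routine adverse-event data for the safety estimand, and secondarily missing weights for Category 3 of the main hybrid. The primary analysis is untouched. On an assumed 1-5%, 3-15 of 300 participants would be affected, with power at or above 96.4% and at most about 0.4 points (8 − 7.6) of attenuation in the hybrid analysis. That last figure supposes that 5% of an active arm leave, all classed in Category 3, and that their true off-drug effect lies between none and the full 8 points. The true frequency is unknown and could be lower, since emergency unblinding is tightly restricted. This is a minor point, worth correcting because it is cheap.

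**What to change.** Reconcile Protocol 6.3, 7.1 and 7.2 with SAP 4.3.3 so that leaving study drug and leaving the study are separate decisions. Which treatment rule applies after a new agent or after unblinding is for the sponsor to decide, and nothing here favours one. Whatever rule is chosen:

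- state that already scheduled collection of weight and adverse events, or at least Visit 99 and Visit 801, continues where the participant consents;
- record the date of unblinding or of the first dose of the new agent, so that the SAP strategies can be applied;
- give both events a row in SAP Table 4.1, so that their category is fixed in advance.

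The visits are already in the Schedule of Activities. The cost is a wording amendment to the protocol, a matching edit to the SAP and, if not already captured, a date field in the case report form.

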7.3. Lost to Follow-Up

A participant will be considered lost to follow-up if he or she repeatedly fails to return for scheduled visits and is unable to be contacted by the study site. Site personnel or designee are expected to make diligent attempts to contact participants who fail to return for a scheduled visit or were otherwise unable to be followed up by the site.

8. Study Assessments and Procedures

- Study procedures and their timing are summarized in the SoA.
- Immediate safety concerns should be discussed with the sponsor immediately upon occurrence or awareness to determine if the participant should continue or discontinue study intervention.
- Adherence to the study design requirements, including those specified in the SoA, is essential and required for study conduct.
- All screening evaluations must be completed and reviewed to confirm that potential participants meet all eligibility criteria. The investigator will maintain a screening log to record details of all participants screened and to confirm eligibility or record reasons for screening failure, as applicable.

8.1. Efficacy Assessments

Primary:

The primary efficacy measure is body weight. Body weight measurements will be collected at specific clinic visits as summarized in the SoA. Methods for measuring body weight are described in Section 10.8.

Secondary:

The following secondary efficacy measures will be collected at the times shown in the SoA.

- BMI (derived using body weight in kilograms divided by the square of height in meters), and
- waist circumference (see Section 10.8).

Exploratory:

The following exploratory efficacy measures will be collected at the times shown in the SoA:

- blood pressure (see Section 4.1.2.3)
- heart rate measured by ABPM (see Section 4.1.2.3)
- lipid parameters
- glycemic control
- mechanistic biomarkers related to insulin sensitivity, pancreatic beta cell function, glucagon receptor target engagement, fatty acid oxidation, lipolysis, purine metabolism, cardiovascular risk, and inflammation (see table in Appendix 10 [Section 10.10]), and
- patient-reported outcomes (see Section 10.11 [Appendix 11]).

8.2. Safety Assessments

Planned time points for all safety assessments are provided in the SoA.

8.2.1. Physical Examinations

For each participant, measurements including height, weight, and waist circumference should be conducted according to SoA, and following the study-specific recommendations included in Section 10.8 (Appendix 8).

A complete physical examination will include, at a minimum, assessments of

- skin, including feet
- cardiovascular
- respiratory
- GI
- neurological systems, and
- thyroid exam.

Investigators should pay special attention to clinical signs related to previous serious illnesses.

8.2.2. Vital Signs

For each participant, vital sign measurements should be conducted according to the SoA and following the study-specific recommendations included in Section 10.8 (Appendix 8).

Any clinically significant findings from vital sign measurement that result in a diagnosis and that occur after the participant receives the first dose of study intervention should be reported to Lilly or its designee as an AE via eCRF.

8.2.3. Electrocardiograms

For each participant, a 12-lead ECG should be collected according to Section 1.3 (for details, please see Section 10.8). Electrocardiograms will initially be interpreted by a qualified physician, the investigator, or qualified designee at the site as soon after the time of ECG collection as possible, and ideally while the participant is still present, for immediate participant management, should any clinically relevant findings be identified. Any clinically significant findings from ECGs that result in a diagnosis and that occur after the participant receives the first dose of the investigational treatment should be reported to Lilly or its designee as an AE via the eCRF. In addition, tracings collected at the baseline, 24, and 48 weeks will be assessed qualitatively by a blinded cardiologist.

8.2.4. Clinical Safety Laboratory Assessments

- See Section 10.2 (Appendix 2) for the list of clinical laboratory tests to be performed and to the SoA for the timing and frequency.
- The investigator must review the laboratory results, document this review, and report any clinically relevant changes occurring during the study as an AE. The laboratory results must be retained with source documents unless a Source Document Agreement or comparable document cites an electronic location that accommodates the expected retention duration. Clinically significant abnormal laboratory findings are those which are not associated with the underlying disease, unless judged by the investigator to be more severe than expected for the participant's condition.

- All laboratory tests with values considered clinically significantly abnormal during participation in the study or within 1 month after the last dose of study drug (Visit 801) should be repeated until the values return to normal or baseline or are no longer considered clinically significant by the investigator or medical monitor.
 - If such values do not return to normal/baseline within a period of time judged reasonable by the investigator, the etiology should be identified, and the sponsor notified.
 - All protocol-required laboratory assessments, as defined in Section 10.2 (Appendix 2), must be conducted in accordance with the SoA, standard collection requirements, and laboratory manual.
- If laboratory values from non-protocol-specified laboratory assessments performed at an investigator-designated local laboratory require a change in participant management or are considered clinically significant by the investigator (for example, SAE or AE or dose modification), then report the information as an AE.

8.2.5. Safety Monitoring

Lilly will periodically review evolving aggregate safety data within the study by appropriate methods. The study team will review safety reports in a blinded fashion (for applicable blinded study period) according to the schedule provided in the Trial-Level Safety Review plan. Lilly will also review SAEs within time frames mandated by company procedures. The Lilly CRP will, as appropriate, consult with the functionally independent Global Patient Safety therapeutic area physician or clinical scientist.

8.2.5.1. Hepatic Safety Monitoring

Close Hepatic Monitoring

Laboratory tests (Section 10.9), including ALT, AST, ALP, total bilirubin, direct bilirubin, gamma-glutamyltransferase, and creatine kinase, should be repeated within 48 to 72 hours to confirm the abnormality and to determine if it is increasing or decreasing, if 1 or more of these conditions occur:

If a participant with baseline results of...	develops the following elevations
ALT or AST <1.5X ULN	ALT or AST ≥3X ULN
ALP <1.5X ULN	ALP ≥2X ULN
TBL <1.5X ULN	TBL ≥2X ULN (except for participants with Gilbert's syndrome)
ALT or AST ≥1.5X ULN	ALT or AST ≥2X baseline
ALP ≥1.5X ULN	ALP ≥2X baseline
TBL ≥1.5X ULN	TBL ≥1.5X baseline (except for participants with Gilbert's syndrome)

If the abnormality persists or worsens, clinical and laboratory monitoring, and evaluation for possible causes of abnormal liver tests should be initiated by the investigator in consultation with the Lilly-designated medical monitor. At a minimum, this evaluation should include physical examination and a thorough medical history, including symptoms, recent illnesses (for example, heart failure, systemic infection, hypotension, or seizures), recent travel, history of concomitant medications (including over-the-counter), herbal and dietary supplements, and history of alcohol drinking and other substance abuse.

Initially, monitoring of symptoms and hepatic biochemical tests should be done at a frequency of 1 to 3 times weekly, based on the participant's clinical condition and hepatic biochemical tests. Subsequently, the frequency of monitoring may be lowered to once every 1 to 2 weeks, if the participant's clinical condition and lab results stabilize. Monitoring of ALT, AST, ALP, and TBL should continue until levels normalize or return to approximate baseline levels.

Comprehensive Hepatic Evaluation

A comprehensive evaluation should be performed to search for possible causes of liver injury if 1 or more of these conditions occur:

If a participant with baseline results of...	develops the following elevations:
ALT or AST <1.5X ULN	ALT or AST \geq 3X ULN with hepatic signs/symptoms*, or ALT or AST \geq 5X ULN
ALP <1.5X ULN	ALP \geq 3X ULN
TBL <1.5X ULN	TBL \geq 2X ULN (except for participants with Gilbert's syndrome)
ALT or AST \geq 1.5X ULN	ALT or AST \geq 2X baseline with hepatic signs/symptoms*, or ALT or AST \geq 3X baseline
ALP \geq 1.5X ULN	ALP \geq 2X baseline
TBL \geq 1.5X ULN	TBL \geq 2X baseline (except for participants with Gilbert's syndrome)

* Hepatic signs/symptoms are severe fatigue, nausea, vomiting, jaundice, right upper quadrant abdominal pain, fever, rash, and/or eosinophilia >5%.

At a minimum, this evaluation should include physical examination and a thorough medical history, as outlined above, as well as tests for prothrombin time (PT)-INR; tests for viral hepatitis A, B, C, or E; tests for autoimmune hepatitis; and an abdominal imaging study (for example, ultrasound or computed tomography [CT] scan).

Based on the participant's history and initial results, further testing should be considered in consultation with the Lilly-designated medical monitor, including tests for hepatitis D virus, cytomegalovirus, Epstein-Barr virus, acetaminophen levels, acetaminophen protein adducts, urine toxicology screen, Wilson's disease, blood alcohol levels, urinary ethyl glucuronide, and blood phosphatidylethanol. Based on the circumstances and the investigator's assessment of the participant's clinical condition, the investigator should consider referring the participant for a

hepatologist or gastroenterologist consultation, magnetic resonance cholangiopancreatography, endoscopic retrograde cholangiopancreatography, cardiac echocardiogram, or a liver biopsy.

Additional Hepatic Data Collection (Hepatic Safety CRF) in Study Participants Who Have Abnormal Liver Tests during the Study

Additional hepatic safety data collection in hepatic safety CRFs should be performed in study participants who meet 1 or more of the following 5 conditions:

1. Elevation of serum ALT to $\geq 5X$ ULN on 2 or more consecutive blood tests (if baseline ALT $< 1.5X$ ULN)
 - In participants with baseline ALT $\geq 1.5X$ ULN, the threshold is ALT $\geq 3X$ baseline on 2 or more consecutive tests
2. Elevated TBL to $\geq 2X$ ULN (if baseline TBL $< 1.5X$ ULN) (except for cases of known Gilbert's syndrome)
 - In participants with baseline TBL $\geq 1.5X$ ULN, the threshold should be TBL $\geq 2X$ baseline
3. Elevation of serum ALP to $\geq 2X$ ULN on 2 or more consecutive blood tests (if baseline ALP $< 1.5X$ ULN)
 - In participants with baseline ALP $\geq 1.5X$ ULN, the threshold is ALP $\geq 2X$ baseline on 2 or more consecutive blood tests
4. Hepatic event considered to be an SAE
5. Discontinuation of study drug due to a hepatic event

Note: The interval between the 2 consecutive blood tests should be at least 2 days.

